Full Protocol

**Retrospective Analysis of the Use of Biologics for Juvenile Idiopathic
Arthritis Related Uveitis in Abou El Reesh Pediatric Hospital, Cairo
University**

Background and introduction

Juvenile Idiopathic Arthritis (JIA) remains, globally, the most common systemic disorder associated with pediatric uveitis. It accounts for approximately 75% of cases of pediatric anterior uveitis (AU) and affects around 30% of ANA positive JIA patients (regardless their type of arthritis).¹ In a cohort study from the Cairo University Pediatric Hospital, JIA accounted for 39% of all cases of pediatric uveitis (unpublished data).

The uveitis, being asymptomatic, chronic and often severe, leads to complications in a large number of patients. Studies estimate that 28–67% of patients with JIA-associated uveitis develop ocular complications, with 12% developing poor visual outcome. The main causes of poor vision were cataract, band keratopathy and macular edema.²

The only means of improving long term effects of uveitis, is early and aggressive anti-inflammatory treatment.³

The main line of treatment of non-infectious causes of uveitis have been topical and systemic corticosteroids. However, it is well known that their prolonged use often leads to ocular and systemic complications, especially in the pediatric age group.⁴

In 2019, the American College of Rheumatology/Arthritis Foundation recommended that in severe active chronic AU or in the presence of sight-threatening complications, methotrexate (MTX) and a monoclonal antibody TNFi should be administered immediately. This is recommended over MTX as monotherapy. They also recommended that inadequate response to one monoclonal TNFi at standard JIA dose, the dose and or frequency should be increased rather than switching to another monoclonal antibody TNFi.⁵

Immunosuppressive drugs are used as steroid-sparing agents but are not free of complications. They increase the susceptibility of children to infection, may cause organ toxicity, reversible bone marrow suppression and may possibly lead to the development of malignancies.³

Thus, our study aims to analyze the use of biologics in our hospital (Abou el Reesh, Cairo University) for children with JIA in controlling their ocular inflammation, prevention of the development of sight threatening complications and if this outweighs their potential associated side effects.

Patients and methods

Population of study & disease condition

Retrograde analysis of data of all patients presented to Aboul Reesh uveitis clinic taking biologics from January 2017- January 2020. In our hospital, the rationale for using biologics was a high frequency of sight-threatening, frequent recurrences of uveitis or intolerance to steroids or other immunosuppressive drugs, with severe adverse reactions.

Sample size:

It is expected to review 250 patients files of Aboul Reesh uveitis clinic to find all JIA patients with ocular inflammation treated with biologics.

Inclusion criteria

1. Both genders
2. Age up to 16 years
3. Diagnosed JIA according to rheumatological criteria with ocular affection
 - Any type of arthritis (oligoarticular, polyarticular, systemic onset, ocular JIA)
 - ANA positive or negative
4. Uncontrolled uveitis or frequent relapses

Exclusion criteria:

1. Patients without definitive diagnosis as JIA

2. JIA patients on biologics without ocular affection (for systemic control) or with uveitis controlled without the use of biologics
4. Patients without adequate duration for follow-up (less than 3 months) or lost follow up data
5. Patients without available data prior to the start biologics (to compare control of the uveitis)

Methodology

Data will be obtained from by retrospective analysis of all files of patients with JIA from the Abou El Reesh ophthalmology outpatient clinic.

The patients with ocular inflammation treated by biologics will be further analyzed.

The data analyzed will divided into pre and post biologic treatment:

In both we will document-

-Baseline BCVA (in logMar notation)

- Grading of ocular inflammation

(Anterior chamber and vitreous cells were graded as +0.5, +1, +2, +3 and +4 according to the guidelines of the Standardization of Uveitis Nomenclature Working Group)

- Number of relapses in one year

- Development of sight threatening complication

- Dose and frequency of systemic, regional and topical steroids

- Other interventions required

Treatment parameters to be analyzed include type, duration and dose of biologic agent used, time taken to reach inflammation control, adverse effects, and time taken to develop those adverse effects.

Improvement or worsening of activity of inflammation was assessed according to the Standardization of Uveitis Nomenclature Group's directions (2 step improvement or worsening of cells/flare)

Treatment was determined as efficacious if one of the following was fulfilled:

1. No relapses or decrease in the number of relapses
2. Decrease in dose of topical or systemic steroids
3. Improvement of BCVA of at least two lines

Statistical analysis plan:

All data will be entered into Excel spreadsheets (Microsoft Corporation, Redmond, WA, USA). All statistical analyses will be performed using IBM SPSS version 22.0 software (IBM Corp., Armonk, NY, USA). Descriptive statistics will be summarized as the mean \pm standard deviation for numerical data, frequencies and percentages for categorical data. The ANOVA -test and Pearson moment correlation will be used to compare the means for the numerical data and to identify correlations between them. Chi-square test will be used to compare categorical data. P-values ≤ 0.05 will be considered statistically significant.

References

- 2) Qian Y, and Nisha R. (2010) Juvenile Idiopathic Arthritis Associated Uveitis. *Curr Opin Ophthalmol.* 21(6): 468–472. doi:10.1097/ICU.0b013e32833eab83

Retrospective Analysis of the Use of Biologics for Juvenile Idiopathic Arthritis Related Uveitis in Abou El Reesh Pediatric Hospital, Cairo University

First version, 1st march 2020

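### Adverse effects would be summarised with no confidence interval and no allowance for unequal follow-up, which gives weak support to the aim of weighing benefit against harm

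*Combined protocol and SAP*

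**What the plan says.** - **Aim** (Background and introduction, last paragraph). After control of inflammation and prevention of complications, the study asks "if this outweighs their potential associated side effects". Harm is part of the study question.
- **Follow-up** (Population of study; Exclusion criteria). The source is patients "taking biologics from January 2017- January 2020". The exclusions include "Patients without adequate duration for follow-up (less than 3 months) or lost follow up data". No maximum and no common length of follow-up is set, and no rule says that the biologic must have been started inside the window.
- **Data on harm and exposure** (Methodology). The treatment parameters to be analysed include "type, duration and dose of biologic agent used" and "adverse effects, and time taken to develop those adverse effects".
- **Analysis** (Statistical analysis plan). Numerical data get a mean ± SD, and the rest get "frequencies and percentages for categorical data". The tests are ANOVA, Pearson correlation and chi-square, at p ≤ 0.05. No confidence interval, person-time rate, censoring method or rule for weighing benefit against harm is named.

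**The concern.** Whether a child had an adverse effect is categorical, so its named summary is a percentage. Children watched for 3 months and children watched for years would share one denominator, and the percentage would mix how often events happen with how long anyone looked.

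The planned analysis of time to adverse effect does not repair this. A mean ± SD of that time uses only the children who had an event. Those without one, who carry much of the information about safety, drop out of the summary, and short follow-up makes the mean short.

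With no interval, a low or zero count in a small series carries no statement of uncertainty. The harm side could look small because follow-up was short or patients were few, and the benefit-against-harm conclusion would lean on that.

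**Working it through.** The plan gives no adverse-effect rate, precision target or analysed sample size, so there is no figure to reproduce. The 250 under Sample size is a count of files to screen. Everything below is illustration under stated assumptions.

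**Inputs from the document:** minimum follow-up 3 months (0.25 years); data window 3 years; 250 files; JIA share of paediatric uveitis 39% (Background).

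**Assumed:** a constant event rate λ of 0.1, 0.2 or 0.5 per patient-year; follow-up no longer than the window; 20, 30 or 50 patients analysed.

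**Step 1. Percentage affected against follow-up.** Share affected by time T = 1 − exp(−λT).

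| λ per patient-year | 3 months | 1 year | 3 years |
|---|---|---|---|
| 0.1 | 2.5% | 9.5% | 25.9% |
| 0.2 | 4.9% | 18.1% | 45.1% |
| 0.5 | 11.8% | 39.3% | 77.7% |

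A 12-fold spread in follow-up (36 / 3 months) moves the percentage by a factor of about 10, 9 and 7 with no change in the true rate. These are extremes. In a mixed cohort at λ = 0.2, half at 3 months and half at 1 year gives (4.9 + 18.1) / 2 = 11.5%; half at 1 year and half at 3 years gives (18.1 + 45.1) / 2 = 31.6%.

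**Step 2. Mean time to event among those affected.** With follow-up T, this is 1/λ − T / (exp(λT) − 1). At λ = 0.2:

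- T = 0.25: 5 − 0.25 / 0.05127 = 0.124 years, about 1.5 months.
- T = 3: 5 − 3 / 0.8221 = 1.35 years, about 16 months.

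The true mean is 1 / 0.2 = 5 years, or 60 months. This summary also follows the length of observation.

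**Step 3. Zero events.** The one-sided 95% upper bound is 1 − 0.05^(1/n): 13.9% for n = 20, 9.5% for n = 30 and 5.8% for n = 50. If the 39% share applied to the 250 files, 250 × 0.39 = 97.5, so about 97 would have JIA. The bound at n = 97 is 3.0%, but the number on biologics is unknown and cannot exceed that ceiling.

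**Step 4. What the fix would show.** Take 5 of 50 patients affected, a crude 10%. The exact (Clopper-Pearson) 95% interval is 3.3% to 21.8%. Taking time at risk as 50 × mean follow-up (slightly too much, since a first-event rate stops the clock at the event), exact Poisson intervals are:

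| Mean follow-up | Patient-years | Per 100 patient-years (95% CI) |
|---|---|---|
| 0.25 years | 12.5 | 40.0 (13.0 to 93.3) |
| 1 year | 50 | 10.0 (3.2 to 23.3) |
| 3 years | 150 | 3.3 (1.1 to 7.8) |

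The same 10% stands for rates that differ 12-fold.

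**The case against.** The strongest reply is that this is a short, descriptive chart review that does not ignore time: biologic duration and time to adverse effect are both listed for analysis. A reader might infer that adverse effects will be reported as crude percentages and nothing else. The document does not support that. What stands is that the method named for those times is a mean ± SD, which leaves out patients without an event (Step 2).

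A reader might also infer that benefit and harm sit on different scales, relapses per year against percent ever affected. That fails. The Methodology defines efficacy as a yes/no outcome met by any one of three criteria, so under the plan it would also be a percentage.

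Nor does the plan say that follow-up runs to 3 years. That comes from the data window; children already on a biologic before January 2017 could have longer exposure, which would widen the spread.

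Finally, rates and intervals would not settle the benefit-harm question by themselves. There is no comparator, adverse effects are not among the items documented both before and after biologics, and no benefit-harm criterion is stated. Because patients are selected for uncontrolled uveitis or frequent relapses, some fall in relapses may be regression to the mean. All of this is fair, and it limits what the fix can claim.

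**Conclusion.** The concern holds as a gap in the analysis plan. The summaries named for adverse effects take no account of unequal follow-up and carry no interval, so they give weak support to a stated aim. Over 3 months to 3 years, the percentage affected could differ about 7- to 10-fold at one true rate, and a series of 20 to 50 patients with no events could not exclude risks of about 6% to 14%. These sizes rest on constant rates, follow-up within the window and sample sizes that are all assumed.

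It would go too far to conclude that the aim cannot be addressed at all. The exposure and timing data listed in the Methodology allow better estimates, so this is a repairable weakness that should be corrected before analysis.

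**What to change.** Amend the Statistical analysis plan as follows.

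1. Report patients with a first adverse effect per patient-year at risk on biologic, with an exact Poisson 95% interval. Patients with an event contribute time to the first one; the others contribute their time on biologic. Counting first events avoids treating repeat events in one child as independent. A Kaplan-Meier cumulative incidence, censored at end of follow-up and with a 95% interval, is an acceptable alternative that does not assume a constant rate.
2. Give the crude percentage with an exact 95% interval, beside the distribution of follow-up.
3. Add a patient-level table of efficacy (yes/no) by adverse effect (yes/no).
4. Keep the benefit-against-harm statement descriptive. It should cite the upper bound on harm and note that there is no comparator and that relapse reduction may partly reflect regression to the mean.

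Separate results for serious events are not part of this change, because the document neither defines seriousness nor lists it for extraction.

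The cost is new plan wording and slightly more analysis, using duration and event timing already listed. The harm estimate will look less precise.

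### The dated cohort sentence selects on being on a biologic in 2017–2020, with no index date or start-date rule, so persisting users may be over-represented by an amount the documents cannot fix

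*Combined protocol and SAP*

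**What the plan says.** The protocol describes the analysed cohort in three places.

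- *Population of study & disease condition*: "all patients presented to Aboul Reesh uveitis clinic taking biologics from January 2017- January 2020". This is the only description with dates.
- *Sample size*: the file review is meant "to find all JIA patients with ocular inflammation treated with biologics". There are no dates, and current use is not required.
- *Methodology*: "The patients with ocular inflammation treated by biologics will be further analyzed", drawn from a "retrospective analysis of all files of patients with JIA from the Abou El Reesh ophthalmology outpatient clinic". Again there are no dates.

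No inclusion criterion mentions when the biologic was started. Two exclusion criteria bear on the point. Criterion 4 removes "Patients without adequate duration for follow-up (less than 3 months) or lost follow up data". Criterion 5 removes "Patients without available data prior to the start biologics".

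The Methodology section plans to report time to inflammation control, adverse effects and time to adverse effects. No time zero is defined for the two time outcomes. The Statistical analysis plan lists descriptive summaries, ANOVA, Pearson correlation and chi-square tests.

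**The concern.** Entry by use during a calendar window is not the same as entry by starting treatment. Children already on drug when the window opens have, by construction, stayed on it until then. Children who started at the same time but left treatment earlier are not seen. If leaving is related to failure or harm, the children who remain look better than all starters would.

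The Background states the aim as judging whether control of inflammation and prevention of complications outweigh the side effects. This kind of selection could favour the drug on both sides of that comparison. None of the listed analyses allows for delayed entry, so the planned statistics would not correct it.

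**Working it through.** **Reading the text.** The plan gives no figure to reproduce. The 250 in the Sample size section counts files to be reviewed, and no number of biologic users, start dates or stopping rate is stated. The first step is to see who qualifies under each description.

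| Child | Dated sentence, plain reading | Undated descriptions |
|---|---|---|
| Started before 2017, still on a biologic in the window | in | in |
| Started before 2017, stopped all biologics before 2017 | **out** | in |
| Failed one biologic before 2017, switched, on another in the window | in | in |
| Started in the window, stopped later in the window | in | in |

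All rows are subject to the other criteria. The descriptions disagree only on the second row, and that is the row where the selection arises. Criterion 5 asks whether pre-treatment records exist, not when treatment began. It may remove some long-standing users, but it cannot bring back those who stopped earlier.

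**Illustrating the possible size.** All of these inputs are assumptions except the 3-year window:

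- Children start at a constant rate over L years before January 2017 and through the 3-year window.
- The stopping hazard is constant, with yearly stopping probability q, so λ = −ln(1 − q).
- The cohort is anyone on drug at any time in the window, and one-year outcomes are taken as fully observed.

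In units of one year's starters:

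- Pre-2017 starters still on drug in January 2017: S = (1 − e^(−λL))/λ.
- Share of pre-2017 starters missed: 1 − S/L.
- Share of the cohort who are pre-2017 starters: S/(S + 3).
- One-year stopping rate in the cohort, for L ≥ 1: (A + 3q)/(S + 3), where A = q/λ − (1 − q). A counts pre-2017 starters who were on drug in January 2017 and stopped within a year of starting.

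Worked case, L = 3 and q = 0.20: λ = 0.2231. S = (1 − 0.512)/0.2231 = 2.187. Missed: 1 − 2.187/3 = 27%. Pre-2017 share: 2.187/5.187 = 42%. A = 0.896 − 0.800 = 0.096. One-year stopping rate: (0.096 + 0.600)/5.187 = 13.4%, against a true 20%.

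| L (years) | Pre-2017 share of cohort, q = 10/20/40% | Pre-2017 starters missed | Cohort one-year stopping rate (true 10/20/40%) |
|---|---|---|---|
| 0 | 0% | none | 10 / 20 / 40% |
| 1 | 24 / 23 / 21% | 5 / 10 / 22% | 8.8 / 17.9 / 36.6% |
| 3 | 46 / 42 / 34% | 14 / 27 / 49% | 6.3 / 13.4 / 30.5% |
| 5 | 56 / 50 / 38% | 22 / 40 / 64% | 5.1 / 11.6 / 28.8% |

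These are stopping rates, not efficacy rates. How far they carry over to efficacy depends on why children stop.

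**Exclusion criterion 4.** This acts on in-window starters too. If stopping also ended follow-up, the 3-month rule would remove 1 − (1 − q)^0.25 of starters: 2.6%, 5.4% or 12.0% for q = 10%, 20% or 40%.

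**The case against.** The strongest reply is that the selection is one possible consequence of loose wording, not a settled feature. The dated sentence could be read as use beginning in January 2017. The two undated sentences would admit past users, including those who stopped. This stands in part: what the documents firmly establish is a missing index date and three descriptions that do not agree. But the dated sentence is the only one that sets a period, and its plain reading does not require a start inside it.

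A reader might infer that failures and drug-related stoppers are left out in general. The documents do not support that. The dated sentence loses only children off all biologics before January 2017. In-window stoppers and children who switched agents remain eligible, subject to criterion 4. Because this is a file review, a pre-2017 starter's earlier adverse effects may also be on record.

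A reader might also try to put a figure on the inflated efficacy. Take a true success rate of 60%, stopping hazards of 0.15–0.25 per year, 1–2 years on drug by January 2017, and pre-2017 starters making up 25–50% of the sample. Observed success would then run from 0.75 × 0.60 + 0.25 × 0.60/e^(−0.15) = 62% to 0.50 × 0.60 + 0.50 × 0.60/e^(−0.50) = 79%. That range should not be used as an estimate. Every input is assumed, and its upper end requires 0.60/0.607 = 99% success among pre-2017 starters. It also counts every stopper as an efficacy failure, although under the protocol's any-one-of-three rule a child who stops for harm can count as a success. If half of the stoppers stopped for harm and succeeded at the same 60% (again assumed), the range would be about 61–70%. If stopping were unrelated to success, there would be no efficacy bias.

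Finally, including established users with a documented baseline is a common compromise in a descriptive single-centre review. That supports reporting them, but not pooling them with starters in the main analysis without separation.

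**Conclusion.** The point holds in a conditional form. The cohort has no index date, and its three descriptions conflict on children who stopped before 2017. On the plain reading of the dated sentence, persistence to January 2017 is a condition of entry for earlier starters.

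Bias towards better efficacy and fewer adverse effects needs two further conditions: pre-2017 starters must be present, and stopping must be related to failure or harm. The documents give information on neither, so a flat statement that efficacy is overstated would go beyond them. The size ranges from zero upwards and cannot be narrowed from the text; the table of stopping rates shows direction and sensitivity only. The change is still worth making, because it uses files already under review and settles every reading of the wording.

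**What to change.** 1. Replace the three descriptions with one cohort definition, with the index date at the first biologic dose. Criterion 5 already presumes that the start is known.
2. Base the main analysis on all children whose first dose falls between January 2017 and January 2020, whether or not they later stopped.
3. Report pre-2017 starters in a separate table, and add a sensitivity analysis that pools both groups.
4. Reconcile criterion 4 with step 2, since as written it removes some starters. Count and describe those removed for under 3 months or lost follow-up, with the reason for stopping and any adverse effects. Keep them in the adverse-effect count where data exist. Separate children whose follow-up is short only because they started late in the window.

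The cost is a smaller main-analysis sample and some extra tabulation. The reduction cannot be computed, because start dates and user counts are not given, but it may matter. If the unpublished 39% JIA share in the Background applied to the 250 files (an assumption), about 0.39 × 250 ≈ 98 files would be JIA, before biologic users are selected. The pooled sensitivity analysis keeps the earlier starters in the report.

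### Efficacy criterion 1 counts a child whose uveitis stays steadily active as a treatment success, because having no relapses is enough on its own and no inactive eye is required

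*Combined protocol and SAP*

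**What the plan says.** Inclusion criteria, item 4, gives two routes of entry joined by an or: "Uncontrolled uveitis or frequent relapses". Neither term is defined.

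Methodology then sets the only efficacy rule in the plan: "Treatment was determined as efficacious if one of the following was fulfilled". The three criteria are:

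- Criterion 1, on the relapse count: "No relapses or decrease in the number of relapses"
- Criterion 2, on steroid use: "Decrease in dose of topical or systemic steroids"
- Criterion 3, on visual acuity: "Improvement of BCVA of at least two lines"

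The data to be recorded before and after the biologic include anterior chamber and vitreous cell grades from +0.5 to +4 and "Number of relapses in one year". What makes an event a relapse is not stated. Just before the efficacy rule, Methodology says that improvement or worsening of activity is judged by a two-step change in cells or flare. That rule is not tied to the word relapse or to any efficacy criterion. The treatment parameters include "time taken to reach inflammation control", but control is not defined and is not an efficacy criterion.

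Background and introduction gives control of ocular inflammation as the first aim. Exclusion criteria, item 5, requires pre-biologic data so that control of the uveitis can be compared.

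**The concern.** A relapse count suits a child who is quiet between attacks. It says little about a child whose eye is active all the time, and item 4 admits children with uncontrolled uveitis. Such a child can remain just as inflamed on the biologic, record no relapses, and meet criterion 1. Because any one criterion is enough, criteria 2 and 3 cannot reverse that result.

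The headline proportion with efficacious treatment could therefore include complete failures on the study's first aim. The design compares each child before and after treatment, with no untreated group against which an inflated rate would stand out. No choice of significance test repairs an outcome that has been misclassified.

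**Working it through.** The plan states no derived figure on this point. The 250 in Sample size is a count of files to be screened, with no rate or power behind it. The check is therefore of the rule's logic, followed by an illustration of size.

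**Step 1. Inputs from the documents.** Two routes of entry (Inclusion criteria, item 4); any-one-of-three rule and its criteria (Methodology); cell grades +0.5, +1, +2, +3, +4 and the two-step activity rule (Methodology); minimum follow-up of 3 months (Exclusion criteria).

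**Step 2. Apply criterion 1 to eyes that are never quiet.** Take every possible sequence of the five active grades over 3, 4 or 5 visits: 5³ = 125, 5⁴ = 625, 5⁵ = 3125. Count the sequences containing a relapse under two readings of the undefined word, treating each listed grade as one step.

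| Visits | Sequences | Relapse = activity after a quiet visit | Relapse = worsening of two or more steps |
|---|---|---|---|
| 3 | 125 | 0 | 59 |
| 4 | 625 | 0 | 404 |
| 5 | 3125 | 0 | 2397 |

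These are counts of possible paths, not probabilities. Under the first reading, every never-quiet child scores no relapses. Under the second, fluctuating eyes can register a relapse, but all 5 constant-grade sequences, steady +3 and +4 among them, still score none. If +0.5 were taken as inactive, 5 − 1 = 4 steadily active sequences would remain and the result is the same.

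**Step 3. Illustrate the size.** Let f be the share of the cohort who stay active without a two-step improvement and meet neither criterion 2 nor criterion 3; q the share of these who score no relapses; s the true success rate in the rest. All three are assumptions.

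- True success rate = (1 − f) × s
- Reported success rate = (1 − f) × s + f × q
- Overstatement = f × q

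With s = 0.70:

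| f | True | Reported, q = 1 | Reported, q = 0.5 |
|---|---|---|---|
| 0.10 | 63% | 73% | 68% |
| 0.30 | 49% | 79% | 64% |
| 0.50 | 35% | 85% | 60% |

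For example, at f = 0.30 and q = 1: 0.70 × 0.70 + 0.30 = 0.79, against 0.49.

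**Step 4. Secondary effect on the pre/post relapse comparison.** Suppose a relapse must follow a quiet period. A child continuously active before the biologic has a prior count of 0. If the biologic brings control and the child later flares once, the count goes from 0 to 1 and looks like worsening. At an assumed flare rate of 0.5 to 1.0 per year (Poisson), the chance of at least one flare in a full year is 1 − exp(−0.5) = 39% to 1 − exp(−1.0) = 63%. Over the 3-month minimum follow-up it is 1 − exp(−0.125) = 12% to 1 − exp(−0.25) = 22%.

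**The case against.** The strongest reply is that the documents do not say that a relapse needs a quiet period before it, or that uncontrolled means continuously active. The clinic's stated reasons for using biologics include frequent recurrences and drug intolerance, and do not name persistent activity. The Background's description ("The uveitis, being asymptomatic, chronic and often severe") is general and does not mean never quiet. Cell grades before and after treatment are collected in any case, so non-response could still be seen. All of this stands as a limit on extent and certainty. None of it removes the defect, because a steadily active eye meets criterion 1 under either reading and the collected grades do not enter the efficacy rule.

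A reader might infer several stronger things that the documents do not support:

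- **That a relapse count can never register anything in a never-quiet eye.** This is exact only if a relapse must follow quiet.
- **That a particular share of the successes are children who never improved.** Assuming 30% to 60% persistently active and 30% to 50% of those never controlled gives 0.30 × 0.30 = 9 to 0.60 × 0.50 = 30 percentage points. The documents support neither input. Never controlled is also not never improved: an eye going from +4 to +1 meets the plan's own two-step rule. Some of these children would qualify anyway through criterion 2 or 3.
- **That the efficacy outcome runs backwards for responders.** A child going from 0 to 1 relapse fails criterion 1 only, and is still efficacious if the steroid dose falls or acuity gains two lines. The percentages in step 4 are therefore not misclassification rates for efficacy.
- **That pooling the two courses shortens time to control.** That would need children who are quiet at the start to be entered as zero, and the plan does not say how they are coded.

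Admitting both courses is also a legitimate choice of cohort. Item 4 brings the affected children in, but the fault lies in criterion 1.

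**Conclusion.** The point holds in this form: as written, criterion 1 classes a child with steadily active uveitis before and after the biologic as a treatment success, and nothing elsewhere in the plan overrides it. This is a stated rule that gives a wrong result on the study's first aim, so it should be corrected before the analysis is run.

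The direction is towards too high a success rate. The size cannot be derived from the documents, because they give neither the share of persistently active children nor a definition of relapse; the figures in step 3 show only how the error scales with f × q. The effect on the pre/post relapse comparison is secondary and depends on the quiet-first reading of relapse.

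**What to change.** - Define relapse and inactivity from the cell grades already recorded, stating which grades count as inactive.
- For each child, record whether uveitis was persistently active or relapsing before the biologic, and whether it was active on the day the biologic started.
- For children persistently active at entry, replace criterion 1 with reaching inactivity or the plan's own two-step improvement. Count relapses only after a documented quiet period.
- For relapsing children, keep the relapse comparison.
- Report time to inflammation control only for children active at the start.
- Show the two courses separately, with the proportion meeting each of the three criteria and the proportion inactive at the last visit. Changing criterion 1 alone would leave still-active eyes that succeed through criterion 2 or 3 hidden in the total; this display makes them visible.

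The cost is one or two extra fields from files that are being reviewed anyway, smaller groups in each table, and probably a lower reported success rate.
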